#### (Fasting Condition)

In each period on each day from Day 1 to Day 5 and from Day 7 to Day 9, the subjects were served the standard breakfast, Lunch, Snacks and dinner at 0.50, 4.00, 8.00, and 12.00 hours post dose. On day 6, lunch, snacks and dinner were served at 4.00, 8.00, and 12.00 hours post dose. Meal plans were identical for both the study periods. On Day 6, water was provided ad libitum during the study, except 1 hour before and 1 hour after dosing except during drug administration.

Drug administration details are provided in the table below.

#### 9.4.6 Blinding

This study was designed as an open label study. However, the bioanalytical scientists who performed the analysis were blinded to the treatment during subject sample analysis to avoid bias.

#### 9.4.7 Prior and Concomitant Therapy

No concomitant medication was administered since there were no AEs recorded in the study.

#### 9.4.8 Treatment Compliance

In each period, from Day 1 to Day 5 and Day 7 to Day 9, the subjects who were assigned B, received LANOXIN® (digoxin) USP 250 mcg + Spironolactone Oral Suspension 100 mg (Carospir® Oral Suspension 20 mL of 25 mg / 5 mL) and subjects who were assigned A were not dosed. All the subjects swallowed the drug as a whole. On Day 6, subjects received a single dose of the Treatment A or Treatment B in each period. All the subjects swallowed the drug as a whole.

The Principal investigator or qualified designate, was responsible for ensuring that the administration of timed oral doses was conducted. Additionally, to ensure subject compliance, study personnel conducted oral cavity check immediately after drug administration.

### 9.5 EFFICACY AND SAFETY VARIABLES

#### 9.5.1 Pharmacokinetic and Safety Measurements Assessed

#### Pharmacokinetic measurements assessed:

The following pharmacokinetic parameters for digoxin were obtained using non-compartmental method (WinNonlin, version 8.1, Pharsight Corporation, USA):  $C_{max}$ , AUC0.96 and  $t_{max}$ 

#### Safety Assessment:

Subjects were monitored for safety during the study and until the completion of the study. Safety assessments were done based on clinical observations, laboratory data at the beginning and at the end of the study and evaluation of the AEs observed during the course of the study.

Screening assessment comprised of detailed demographic data and medical history followed by general physical examination and systemic examination and laboratory investigations (hematology, biochemistry, urine analysis and serology), vitals, ECG

#### (Fasting Condition)

(done within 28 days prior to check in of period one), 2D echo and chest X-ray (done within 6 months prior to check in of period one).

Subjects were monitored for safety during the entire study. The subject's Clinical examination along with vital signs (seated blood pressure, radial pulse rate and oral/aural temperature) were measured during check-in and check-out of each period.

Clinical examination was done on prior to dosing on Day 06 in each study period. Oral/aural temperature was measured prior to dosing in each study period.

Vital parameters – seated blood pressure and radial pulse rate were measured at prior to dosing, 1.00, 3.00, 5.00 and 11.00 hours post dose in each period from Day 1 to Day 5, and from Day 6 to Day 9, vitals were measured prior to dosing, at 1.00, 2.00, 3.00, 5.00, 8.00 and 11.00 hours post dose in each period.

Note

- On Day 6 the Vital signs (i.e. up to 3.00 hours post dose) was performed at bed side.
- For subjects who were randomized to treatment A, the vitals were checked at 5.00 hours post dose during day 1 to Day 5.

ECG was performed at 1.00 and 3.00 hours post dose in each period on Day 6, before period II check-in for subject study eligibility and at check-out of each period of the study.

In each study period creatinine clearance and serum potassium levels were measured on Day 05 for the dosing eligibility of the subjects.

For the safety of the subjects, hematology (except blood grouping and Rh typing) and biochemistry (except random blood sugar) investigations were repeated at the end of the study.

## 9.5.2 Appropriateness of Measurements

The blood sampling points were chosen such that  $T_{max}$  could be accurately characterized for digoxin. In addition, sampling was done up to 96.00 hours post dose such that the plasma concentration could be measured for adequately profiling the pharmacokinetics of the product.

All safety assessments chosen were standard and widely used and are documented in the appropriate section of the case report forms (CRFs).

#### 9.5.3 Primary Pharmacokinetic Variable(s)

The primary pharmacokinetic variables calculated in the study were  $C_{max}$  and  $AUC_{0.96}$  for digoxin. The absence of drug-drug interaction was based on the 90% Confidence Intervals (CI) of the above parameters.

(Fasting Condition)

Confidential

## 9.5.4 Drug Concentration Measurements

#### 9.5.4.1 Blood Sampling

On Day 6, a total of 25 (1 x 5 mL) blood samples were collected for each subject in pre-specified vacutainer tubes containing anticoagulant ( $K_2EDTA$ ) in each study period. The pre-dose sample was collected within 2 hours prior to drug administration. The post-dose blood samples were collected at 0.25, 0.50, 0.75, 1.00, 1.33, 1.67, 2.00, 2.33, 2.67, 3.00, 3.50, 4.00, 5.00, 6.00, 8.00, 10.00, 12.00, 16.00, 24.00, 36.00, 48.00, 60.00, 72.00 and 96.00 hours in each study period.

Note: Blood samples up to 3 hours post dose were collected at bed side.

The pre-dose and post-dose samples up to 24.00 hours were collected via an indwelling cannula placed in an ante-cubital vein or one of the forearm veins inserted prior to first sample collection in each period and 36.00, 48.00, 60.00, 72.00 and 96.00 post dose samples were collected by a fresh vein-puncture.

All the blood draws up to 96.00 hours were done in-house. The collected blood was transferred immediately after collection in vacutainer tubes containing anticoagulant ( $K_2EDTA$ ) in each of the two study periods.

#### Sample Processing:

The vacutainers containing blood samples obtained from the subjects were centrifuged in a refrigerated centrifuge at 4000 rpm for 10 minutes at 4°C. The separated plasma was transferred to pre-labeled polypropylene tubes to make equal aliquots, for all the samples.

#### **Blood volume:**

The total volume of blood collected during the entire study did not exceed 292 mL for each subject. However, additional blood (3-5 mL) would be collected for repeat/ additional investigations when significant abnormalities in the laboratory investigations were observed.

#### Sample Storage and Shipping:

All plasma samples were stored in a freezer at a temperature of  $-20 \pm 5^{\circ}$ C up to 4.00 hours and then were transferred to  $-70 \pm 15^{\circ}$ C at the clinical site. Prior to shipping, the samples were packed into thermal insulated containers and packed in sufficient dry ice to assure that they remained frozen and were protected from breakage during shipment. The plasma samples were transferred from cold chain management (CCM) department to bioanalytical facility on 23 Apr 2019 for analysis batch wise as per approved sequence schedule, after the completion of clinical phase.

#### 9.5.4.2 Urine Sampling

On Day 6, a total of 11 urine samples were collected from each subject in each study period at intervals of (0.00-1.00), (1.00-2.00), (2.00-4.00), (4.00-6.00), (6.00-8.00),

#### (Fasting Condition)

(8.00-12.00), (12.00-16.00), (16.00-24.00), (24.00-48.00), (48.00-72.00) and (72.00-96.00) hours post dose.

Immediately out of the total volume of urine collected at each collection time interval, approximately 10 mL (2 x 5 mL aliquots) of urine samples were transferred into two pre-labeled containers for analysis. They were stored at deep freezer maintained at-20°C or lower until dispatched from Clinical Unit to Bioanalytical Department on 24 May 2019 for analysis. The analysis was done after the completion of clinical phase.

The urine samples were stored at -20°C or lower in the Bioanalytical facility until analysis. After collecting the urine samples from all the subjects at each collection time interval, the total pooled volume was recorded.

#### 9.5.4.3 Method of Measurement

The plasma and urine samples were shipped to the bioanalytical facility of ClinSync Clinical Research Pvt Ltd, Hyderabad, India, where the samples were analyzed to determine the drug concentrations. The drug concentrations were determined from all the plasma samples received from the clinical phase using a validated LC-MS/MS method.

## 9.6 DATA QUALITY ASSURANCE

A systematic and independent examination of study activities and documents was conducted to determine whether the activities were conducted, and the data were recorded, analyzed, and accurately reported according to the protocol, Standard Operating Procedures (SOPs), Good Clinical Practice (GCP), Good Laboratory Practice (GLP) and other applicable regulatory requirement(s).

The quality assurance unit audited every phase of the study from enrollment of subjects into the study to the accurate and completeness of the final reports. The QA statement/declaration is given in Appendix 16.1.8.

## 9.7 STATISTICAL METHODS PLANNED IN THE PROTOCOL AND DETERMINATION OF SAMPLE SIZE

#### 9.7.1 Statistical and Analytical Plans

#### 9.7.1.1 Pharmacokinetic Analysis

Pharmacokinetic parameters for digoxin was calculated from the plasma concentration data and urine data were obtained from all the subjects who completed both the periods, using standard, non-compartmental methods with WinNonlin® Software (version 8.1, Pharsight Corporation, USA). The definition and method of determination for each pharmacokinetic variable is summarized as follows:

Confidential

Primary Pharmacokinetic parame	ters in plasma
C max	Maximum measured plasma concentration.
AUC 0-96	Area under the plasma concentration versus time curve from time 0 to the 96 hour time point concentration.
Secondary Pharmacokinetic parar	neters
T max	Time to achieve maximum plasma concentration. If the maximum value occurs at more than one time point, $T_{max}$ is defined as the first time point with this value.

Pharmacokinetic parameters in urine

CLr	Renal clearance Ae0-240h/AUC0-240 h
fe	Unchanged drug excreted in urine

Concentration-time data that were below limit of quantification were treated as zero for calculations and summary statistics.

Pharmacokinetic analyses included data from samples of subjects who completed both periods of the study.

Descriptive statistics for concentration data were presented for scheduled (nominal) sampling times. Actual elapsed times were used for all pharmacokinetic and statistical analyses only if the samples were withdrawn outside of the permitted window period.

Samples lost / not received from the clinical site, samples processing or arising due to drop out or withdrawal of subjects were to be denoted by the character "M" and excluded from pharmacokinetic analysis.

#### 9.7.1.2 Statistical Analysis

Statistical analysis was performed using the SAS® software version 9.3 (SAS Institute Inc., Cary NC, USA) for digoxin. The following summary statistics for the pharmacokinetic parameters were calculated for both the Treatment A and Treatment B: Number of Subjects (N), Arithmetic Mean (Mean), Standard Deviation (SD), Minimum, Maximum, Median and Percentage Coefficient of Variation (CV%). Additionally, Geometric Mean (GM) was estimated for  $C_{max}$  and  $AUC_{0.96}$ .

The log transformed pharmacokinetic parameters ( $C_{max}$  and  $AUC_{0.96}$  for digoxin) were analyzed using Type III sum of squares, with the main effects of formulation, period, sequence and subjects nested within sequence as random effect. The 90% confidence intervals for the difference between drug formulation least-square means

Confidential

(Fasting Condition)

Confidential

(LSM) were calculated for the parameters  $C_{max}$  and  $AUC_{0.96}$  using log transformed data.

## 9.7.2 Determination of Sample Size

A total of 28 healthy human adult subjects were included in the study. Additionally, 04 stand-by subjects were included in order to dose 28 subjects in period I. As the same perpetrator (LANOXIN® Tablets USP 250 mcg) would be given to both the treatments and only the difference could be with and without spironolactone oral suspension, 28 subjects along with 04 stand-by subjects would be sufficient to provide a reliable estimate of the magnitude and variability of the interaction.

#### 9.8 CHANGES IN THE CONDUCT OF THE STUDY OR PLANNED ANALYSES

There were no changes in the clinical conduct of the study or planned analyses. The study was conducted as per the IEC approved Protocol.

(Fasting Condition)

Confidential

## **10. STUDY SUBJECTS**

### **10.1 DISPOSITION OF SUBJECTS**

A total of 28 + 04 (standby subjects) healthy adult human male subjects were enrolled in the study. All these 28 subjects were dosed in Period-1 and Period-11 of the study.

The following table summarizes the subject disposition:

#### Table 9: Subject disposition (All Subjects)

	Sequence 1	Sequence 2	All
	AB	BA	Subjects
Subjects			
Randomized	14	14	28
Completed	14	14	28
Discontinued	00	00	00

Treatment A: LANOXIN® (digoxin) USP 250 mcg (substrate drug)

Treatment B: LANOXIN® (digoxin) USP 250 mcg + Spironolactone Oral Suspension 100 mg (Carospir® Oral Suspension 20 mL of 25 mg / 5 mL)

#### **10.2 PROTOCOL DEVIATIONS**

Protocol Deviations occurred during the entire duration of the study was presented in the Appendix 16.2.2.

#### **Sample Centrifuge Deviation**

The 0.25 hr sample in period I was centrifuged 45 minutes beyond the scheduled time of blood sample collection

#### **Blood Sample Collection Deviations**

There were three sample collection deviations reported in this study.

#### 11.00 hours post dose vitals Deviations

There were seven post dose vitals deviations were recorded in this study.

Confidential

## **11. PHARMACOKINETIC EVALUATION**

#### 11.1 DATA SETS ANALYSED

A total of 28 subjects were dosed and randomized. All these 28 subjects had evaluable pharmacokinetic parameters for both the periods 1 and 2 and were included in Pharmacokinetic analysis.

Pharmacokinetic analysis was performed on plasma concentration data and urine concentration data from subject nos. 01 - 28.

#### **11.2 DEMOGRAPHIC AND OTHER BASELINE CHARACTERISTICS**

A total of 28 subjects were enrolled in this study. All subjects were healthy human adult male subjects of South Asian race (Indian). Their mean ( $\pm$ SD) age was 28.86  $\pm$  3.51 years (range 20 to 35), mean ( $\pm$ SD) height, weight and BMI were 169.21  $\pm$  5.79 cms (range 156 to 180), 66.50  $\pm$  4.11 kg (range 60.50 to 74.20) and 23.27  $\pm$  1.68 kg/m^2 (range 19.61 to 24.86) respectively.

A table detailing the subject wise demographic characteristics is given in Appendix 16.2.4.

#### **11.3 MEASUREMENTS OF TREATMENTS COMPLIANCE**

Treatment compliance was measured by analysis of plasma and urine samples to determine the concentration of digoxin following the administration of Treatment A and Treatment B.

The assessment of treatment compliance was performed as given under section 9.4.8. The analysis of the clinical samples was performed as explained under section 9.5.4. The details of the validated methods are provided in separate method validation report given in Appendix 16.5.

The samples were analyzed using the above validated method.

The quality control samples were prepared and distributed between subject samples in each analytical run both in the presence and absence of spiranolactone and its metabolite canrenone.

Quality Control samples were analyzed with samples in order to monitor the accuracy and precision of the validated method to ensure that the method continues to perform satisfactorily. The details of the subject analysis are provided in a separate bioanalytical report given in Appendix 16.5.

(Fasting Condition)

Confidential

### 11.4 PHARMACOKINETIC RESULTS AND TABULATIONS OF INDIVIDUAL SUBJECT DATA

#### 11.4.1 Pharmacokinetic & Statistical Analysis

Pharmacokinetic analysis of the plasma and urine concentrations for digoxin was carried out for Treatment A and Treatment B to determine the following PK parameters in each individual subject using Phoenix WinNonlin version 8.1. The results are given below:

Concentration-time data that are below limit of quantification were treated as zero for calculations and summary statistics.

Summary statistics for concentration data were presented for scheduled (nominal) sampling times while actual elapsed times were used for all pharmacokinetic and statistical analyses unless the samples were withdrawn within the permitted window period.

The mean concentration-time profiles of digoxin in plasma after administration of Treatment A and Treatment B are presented in Figure 1 and Figure 2 respectively. Summary statistics of PK parameters per treatment for digoxin are shown in Table 10.

Summary statistics of pharmacokinetic profile of digoxin (substrate drug) in the presence and absence of spironolactone (perpetrator) was provided based on plasma and urine data. Renal clearance (CLR)/Percent Recovered and unchanged drug excreted in urine (fe)/ Amount Recovered for digoxin was measured and provided as a supporting data (evidence) in Table 12.

All the subjects included in the pharmacokinetic analysis had sufficient quantifiable concentrations versus time and no exclusions were considered with respect to pharmacokinetic analysis.

(Fasting Condition)

Confidential

Figure 1 Mean Plasma concentration vs time profiles - treatment wise of digoxin (Linear graph)

[figure not shown]
[figure not shown]

Figure 2 Mean Plasma concentration vs time profiles - treatment wise of digoxin (Semi-log graph)

Protocol No. C-CMP-SPI-001

Confidential

Treatment	Statistics	C max (ng/mL)	AUC 0-96 (ng.hr/mL)	T max (h)
	N	28	28	28
	Mean	1530.188	13715.974	0.744
-	SD	502.810	2669.003	0.195
Treatment A	Min	644.613	8632.172	0.500
atme	Median	1429.822	13440.345	0.750
Trea	Max	2734.608	21455.761	1.330
	Geometric Mean	1456.085	13473.043	0.721
-	CV % Geometric Mean	32.993	19.431	25.996
Treatment	Statistics	C max (ng/mL)	AUC 0-% (ng.hr/mL)	T max (h)
	N	28	28	28
	Mean	2432.908	16551.500	0.901
م	SD	870.562	4108.500	0.569
Jent	Min	539.707	6373.657	0.500
Treatment B	Median	2422.385	17151.091	0.750
Tr	Max	5044.130	23997.624	3.500
	G. Mean	2254.118	15996.644	0.810
	G.mean %CV	45.789	28.453	44.310

Table 10: Summary Statistics for Untransformed Pla	sma PK Parameters of digoxin Per
Treatment	

Treatment A: LANOXIN® (digoxin) USP 250 mcg (substrate drug)

Treatment B: LANOXIN® (digoxin) USP 250 mcg + Spironolactone Oral Suspension 100 mg (Carospir® Oral Suspension 20 mL of 25 mg / 5 mL)

The median time to reach peak plasma concentration  $(T_{max})$  for digoxin was 0.750 hr and 0.750 hr following administration of Treatment A and Treatment B respectively. The  $T_{max}$  ranged from 0.500 to 1.330 hr and 0.500 to 3.500 hr for Treatment A and Treatment B respectively.

The exposure ( $C_{max}$  and  $AUC_{0.96}$ ) of digoxin was not comparable for the Treatment A and Treatment B. The geometric mean  $C_{max}$  was 1456.085 and 2254.118 ng/mL for Treatment A and Treatment B respectively. The geometric mean  $AUC_{0.96}$  was 13473.043 and 15996.644 ng.hr/mL for Treatment A and Treatment B respectively.

(Fasting Condition)

Confidential

## **Drug-Drug Interaction (DDI)**

Statistical analysis was performed to assess the DDI as mentioned in Section 9.7.1. Geometric means, Geometric mean ratio and 90% Confidence intervals for Treatment A and Treatment B are provided in Table 9. The 90% confidence intervals of the geometric mean ratio (Treatment A / Treatment B) for  $C_{max}$  and  $AUC_{0.96}$  were not within standard BE limits.

## Table 11 Summary of Statistical Analysis of Ln-transformed Pharmacokinetic Parameters of digoxin

РК	Geometric L	east Square Me	ans and It's Ratio			
Parameters (Unit)	Treatment A	Treatment B	(Treatment A / Treatment B) (%)	ISCV (%)	90% CI	Power (%)
C max (ng/mL)	1456.085	2254.118	64.597	40.07	54.18% to 77.02%	67.47
AUC 0-96 (ng.hr/mL)	13473.043	15996.644	84.224	18.56	77.45% to 91.59%	99.56

Treatment A: LANOXIN® (digoxin) USP 250 mcg (substrate drug)

Treatment B: LANOXIN® (digoxin) USP 250 mcg + Spironolactone Oral Suspension 100 mg (Carospir® Oral Suspension 20 mL of 25 mg / 5 mL)

#### Cmax and AUC0-96:

The Treatment A was compared to the Treatment B with respect to the pharmacokinetic variables  $C_{max}$  and  $AUC_{0.96}$  for digoxin using an analysis of variance with Treatment, period, sequence and subject nested within sequence effects after a logarithmic transformation of the data. Point estimates and 90% confidence intervals for the "Treatment A / Treatment B" mean ratios of these variables were calculated.

## Table 12 Summary Statistics for Untransformed Urine PK Parameters of digoxin Per Treatment

Treatment	Statistics	Renal clearance (CLR)/Percent Recovered	unchanged drug excreted in urine (fe)/ Amount Recovered
	N	28	28
	Mean	54.687	136717.72
I A	SD	29.158	72895.492
Treatment	Min	22.180	55449.800
atm	Median	46.111	115277.98
Tre	Max	147.642	369104.30
	G. Mean	49.042	122606.02
	G.mean %CV	48.257	48.257

Treatment	Statistics	Renal clearance (CLR)/Percent Recovered	unchanged drug excreted in urine (fe)/ Amount Recovered
	N	28	28
	Mean	53.378	133446.07
B	SD	21.256	53141.044
Jeni	Min	21.641	54103.200
Ireatment	Median	51.185	127962.08
Tre	Max	95.602	239003.90
	G. Mean	49.410	123523.87
	G.mean %CV	42.201	42.201

Treatment A: LANOXIN® (digoxin) USP 250 mcg (substrate drug)

Treatment B: LANOXIN® (digoxin) USP 250 mcg + Spironolactone Oral Suspension 100 mg (Carospir® Oral Suspension 20 mL of 25 mg / 5 mL)

The Renal clearance (CLR)/Percent Recovered and unchanged drug excreted in urine (fe)/ Amount Recovered of digoxin was comparable for the Treatment A and Treatment B. The geometric mean Renal clearance (CLR)/Percent Recovered was 49.042 and 49.410 for Treatment A and Treatment B respectively. The geometric mean unchanged drug excreted in urine (fe)/ Amount Recovered was 122606.02 and 123523.87 for Treatment A and Treatment B respectively.

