## 11.4.7 Pharmacokinetic Conclusions

The % Treatment A / Treatment B ratio of digoxin was 64.597% and 84.224% for  $C_{max}$  and AUC0.96 respectively. The lower and the upper limits at 90% confidence interval were 54.18% - 77.02% and 77.45% - 91.59% for  $C_{max}$  and AUC0.96 respectively, which is not within the standard equivalence limit of 80.00-125.00%. Based on the above results presence of drug-drug interaction is established between digoxin and spironolactone.

By comparing  $C_{max}$  and  $AUC_{0.96}$  plasma values of Treatment A and Treatment B, we conclude that these values were increased by 35% and 16% respectively for Treatment B

The Renal clearance (CLR)/Percent Recovered and unchanged drug excreted in urine (fe)/ Amount Recovered of digoxin was comparable for the Treatment A and Treatment B. The geometric mean Renal clearance (CLR)/Percent Recovered was 49.042 and 49.410 for Treatment A and Treatment B respectively. The geometric mean unchanged drug excreted in urine (fe)/ Amount Recovered was 122606.02 and 123523.87 for Treatment A and Treatment B respectively.

Protocol No. C-CMP-SPI-001

Confidential

(Fasting Condition)

Confidential

By comparing these values, we conclude that there is not much difference between Treatment A and Treatment B, with respect to Renal clearance (CLR)/Percent Recovered and unchanged drug excreted in urine (fe)/ Amount Recovered.

Confidential

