### 2.2.3 Pharmacokinetics

### Absorption

Following oral administration, peak serum concentrations of digoxin occur at 1 to 3 hours. Absorption of digoxin from Digoxin Tablets has been demonstrated to be 60% to 80% complete compared to an identical intravenous dose of digoxin (absolute bioavailability). When Digoxin Tablets are taken after meals, the rate of absorption is slowed, but the total amount of digoxin absorbed is usually unchanged. When taken with meals high in bran fiber, however, the amount absorbed from an oral dose may be reduced.

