### Elimination

### .} ClinSync

Protocol for Drug-Drug Interaction Study of Spironolactone and Digoxin (Fasting Condition) Confidential

Elimination of digoxin follows first-order kinetics (that is, the quantity of digoxin eliminated at any time is proportional to the total body content). Following intravenous administration to healthy volunteers, 50% to 70% of a digoxin dose is excreted unchanged in the urine. Renal excretion of digoxin is proportional to glomerular filtration rate and is largely independent of urine flow. In healthy volunteers with normal renal function, digoxin has a half-life of 1.5 to 2.0 days. The half-life in anuric patients is prolonged to 3.5 to 5 days.

Pharmacokinetic Parameters:

Parameters	Digoxin
T max (hours)	1 - 3
Mean terminal T 1/2 (days)	1.5 - 2.0

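### At least one Treatment A urine recovery (147.6% of the 250 mcg dose) is physically impossible, yet the urine comparison includes it without comment

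*Protocol*

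**What the plan says.** Table 12 in study report section 11.4.1 summarises urine data for all 28 subjects in each treatment. The first data column is labelled both as renal clearance and as percent recovered; the second is labelled "unchanged drug excreted in urine (fe)/ Amount Recovered". The rows that matter here are:

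- Treatment A: "Mean 54.687 136717.72" and "Max 147.642 369104.30".
- Treatment B: "Max 95.602 239003.90".

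Synopsis Tables 4 and 5 carry the same figures. Section 11.4.1 states that nothing was excluded from the pharmacokinetic analysis, and section 11.4.2 has no analysis issue to report.

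The Synopsis conclusion and sections 11.4.1, 11.4.7 and 13 call the urine results comparable. Section 11.4.7 adds: "we conclude that there is not much difference between Treatment A and Treatment B, with respect to Renal clearance (CLR)/Percent Recovered". No confidence interval accompanies the statement.

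Protocol section 2.2.3 gives general background figures for digoxin. On tablets: "Absorption of digoxin from Digoxin Tablets has been demonstrated to be 60% to 80% complete". After intravenous dosing in healthy volunteers: "50% to 70% of a digoxin dose is excreted unchanged in the urine". The half-life is given as 1.5 to 2.0 days.

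**The concern.** Cumulative urinary recovery of unchanged drug cannot exceed the dose. A reported maximum well above 100% means that an input to the calculation (a volume, a concentration, a dilution factor or a sample identity) is wrong for at least one subject in one period. The same value feeds the Treatment A mean, SD and geometric mean.

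Renal handling of digoxin is a stated secondary objective, and the SAP presents the urine data as supportive. A descriptive claim of similarity that rests on an unflagged impossible value should not stand unqualified. The protocol and SAP have a plausibility rule for plasma (pre-dose concentration above 5% of Cmax) but none for urine, so nothing in the plan would have caught it.

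**Working it through.** **1. Reproduce the printed figure.** The dose is one 250 mcg tablet (Protocol 6.1), or 250,000 ng. Percent recovered = amount / 250,000 × 100.

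- A maximum: 369104.30 / 250,000 = 147.64% (printed 147.642).
- A mean: 136717.72 / 250,000 = 54.69% (printed 54.687).
- B maximum: 239003.90 / 250,000 = 95.60% (printed 95.602).

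Across mean, SD, minimum, median, maximum and geometric mean in both treatments, amount divided by percent lies between 2499.98 and 2500.05. The two columns also share the same geometric CV (48.257 in A, 42.201 in B). So the first column is percent of dose, and the amounts, printed without a unit, are in ng. The agreement between columns, and between the Synopsis and Table 12, rules out a misread digit.

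**2. Size of the excess.** 369.1 − 250 = 119.1 mcg more than was given.

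**3. Could extra drug have been present?**

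- Extra dose: section 9.4.1 says Treatment A subjects were not dosed on the other days. Table 7 records 28 tablets dosed per period, and 300 − 2 × 28 = 244 remaining, as printed. Section 9.4.8 describes digoxin on additional days for Treatment B, which conflicts with 9.4.1 and must be reconciled, but it does not concern Treatment A.
- Carry-over: the Day 6 doses were on 16 March and 13 April 2019, 28 days apart. At a 2-day half-life, 250 × 2^(−28/2) = 0.015 mcg remains.

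Neither accounts for 119 mcg.

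**4. What the protocol's background figures imply.**

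- Total urinary recovery of an oral dose: 0.60 × 0.50 = 30% to 0.80 × 0.70 = 56%.
- By 96 h, assuming simple first-order elimination: 30% × (1 − 2^(−96/48)) = 22.5% to 56% × (1 − 2^(−96/36)) = 47.2%.

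The reported 96 h means (54.7% and 53.4%) lie above the 96 h range but inside the total range.

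**5. Effect on the comparison.**

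- As reported: B/A = 49.410 / 49.042 = 1.008.
- A geometric mean without the maximum: exp[(28 ln 49.042 − ln 147.642)/27] = 47.08.
- That subject's Treatment B value, b, is not in the text I read, but it must lie within the reported B range of 21.641 to 95.602. B geometric mean without it: exp[(28 ln 49.410 − ln b)/27].
  - b = 21.641 gives 50.94, so B/A = 50.94 / 47.08 = 1.082.
  - b = 95.602 gives 48.22, so B/A = 48.22 / 47.08 = 1.024.

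With the subject dropped from both periods, B/A is therefore about 1.02 to 1.08.

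Within Treatment A, removing the value takes the arithmetic mean from 54.69% to (28 × 54.687 − 147.642)/27 = 51.24%, and the SD from 29.16 to 23.20.

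**The case against.** The strongest reply is that a single value is shown to be wrong, in a secondary and descriptive part of the report, and that the paired check leaves the two treatments close. That stands, and it limits how far the point can go. Several stronger readings are tempting, and the documents do not support them.

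- **The 80% bioavailability figure as a ceiling.** A reader might infer that every recovery above 80%, including the Treatment B maximum, is also impossible. The protocol gives a general range for tablets, not an individual maximum, and does not state it for dosing with spironolactone. Only 100% of dose is an absolute limit.
- **A reversal of direction.** Removing the maximum takes the Treatment A arithmetic mean from above B's 53.38% to below it. But the report's conclusion cites geometric means, where A (49.042) is already below B (49.410).
- **A ratio of 1.049.** This comes from 49.410 / 47.08, which drops the subject from A but keeps the same subject in B. In a crossover the paired range in the working is the relevant figure.
- **A failed argument about mechanism.** The report's text does not use the urine data to claim that the plasma increase is non-renal.
- **A known cause.** Study report 9.5.4.2 says: "After collecting the urine samples from all the subjects at each collection time interval, the total pooled volume was recorded". This could mean a volume pooled across subjects, but equally each subject's pooled voids within an interval. The documents do not settle the cause.

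The individual urine listings, Appendix 16.2.6 and the bioanalytical report were not in the text I read. A comment on this value may exist there, so only the text I read can be called silent.

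**Conclusion.** The point holds for at least one Treatment A subject-period: 147.6% of dose, an excess of 119.1 mcg. It rests on the single 250 mcg dose and on the constant ratio between the two table columns; the percentage does not depend on the missing unit.

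The other high values are grounds for a query only. The 96 h expectation of about 22% to 47% relies on general background ranges and a first-order approximation.

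The effect on the comparison is modest, and the paired range assumes that only this subject is removed and that the reported Treatment B range is correct. It does not show that the treatments differ in urinary recovery. It shows that the comparability statement was made on data containing an impossible value and needs qualifying. This should be fixed, but it is not critical: the interaction conclusion rests on Cmax and AUC0-96 and is untouched.

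**What to change.** 1. Trace every subject-period with recovery above 100% of dose to its interval volumes, measured concentrations, dilution factors and sample identity, and correct it at source. Query the Treatment B maximum and the generally high 96 h recoveries in the same pass.
2. If a value cannot be corrected, annotate Tables 4 and 12. Show the urine results with and without that subject, dropped from both periods. Presenting both is preferable to a silent exclusion, because neither the protocol nor the SAP has a rule that would exclude this value.
3. Until then, qualify the comparability statement in the Synopsis and in sections 11.4.1, 11.4.7 and 13.
4. Add a check for cumulative recovery above dose to the urine analysis.

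The cost is one source-data query and re-issued urine tables and text, with no new samples. Rewording the collection instructions in Protocol 6.4 may help a later study but cannot repair data already collected.
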